
Study Design
	
This is a randomized controlled trial designed to test efficacy of 4Q-TAP against TEA (routine of care) on quality of recovery 48 hours after CRS-HIPEC surgery. All patients will be enrolled at MD Anderson Cancer Center.

Number of Patients
	
160 patients randomized to the 2 study arms (80 patients per arm)

Sites
	
MD Anderson Cancer Center

Duration of Study	It is expected that this will take up to 36 months.
Duration of Patient Participation	Patients who consented to participate in the study will remain in the study until last planned outcome is collected on postoperative day 30. Patient will have the opportunity to withdraw from the study at any time.
Primary Endpoint Definition	Quality of recovery (QoR) 48 hours after CRS-HIPEC surgery.
Secondary Endpoints	
 
• Postoperative pain 48 hours
 
• The total opioid consumption within 48 hours after surgery
 
• Length of stay
 
• Incidence of adverse events
 
• Incidence of opioid-related adverse events
 
• Postoperative complications and morbidity
 
• QoR on postoperative day 3, 7 10 and 30.
 

Primary Safety Endpoint	All reported adverse events.
Follow-Up Schedule	The study will be considered complete after all randomized patients have had 30 days of follow-up data collection.
Inclusion Criteria	
 
1. Written informed consent;
 
2. 18 years old or older;
 
3. American Society of Anesthesiologists physical status (ASA) 1-3;
 
4. Scheduled surgery: open elective CRS-HIPEC;
 
5. Able to complete the QoR 15 questionnaire;
 
6. Patients scheduled to receive intraoperative chemotherapy;
 

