## 3. STUDY AIMS

a. **Primary Aim:** To compare the efficacy of 4 quadrants TAP blocks (4Q-TAP) versus Thoracic Epidural Analgesia (routine care) on the quality of recovery 48 hours after CRS-HIPEC surgery.

**Hypothesis:** The quality of recovery with 4 quadrants TAP blocks (4Q-TAP) 48 hs after CRS-HIPEC surgery is not inferior to Thoracic Epidural Analgesia (routine care).

b. **Secondary Aim 1:** To compare the efficacy of 4 quadrants TAP blocks (4Q-TAP) versus Thoracic Epidural Analgesia (routine of care) on

postoperative pain 48 hours after CRS-HIPEC surgery.

**Hypothesis:** Postoperative pain 48 hours after CRS-HIPEC surgery is not inferior with 4 quadrants TAP blocks (4Q-TAP) than Thoracic Epidural Analgesia (routine care).

c. **Secondary Aim 2:** To compare the total opioid consumption between patients with 4 quadrants TAP blocks (4Q-TAP) versus Thoracic Epidural Analgesia (routine care) intraoperatively and up to 48 hours after CRS-HIPEC surgery.

**Hypothesis:** Perioperative opioid consumption after CRS-HIPEC surgery is not higher in patients with 4 quadrants TAP blocks (4Q-TAP) than epidural analgesia (routine care).

d. **Secondary Aim 3:** To compare the length of stay (LOS) between patients with 4 quadrants TAP blocks (4Q-TAP) versus Thoracic Epidural Analgesia (routine care) after CRS-HIPEC surgery.

**Hypothesis:** The LOS after CRS-HIPEC surgery is shorter in patients with 4 quadrants TAP blocks (4Q-TAP) than Thoracic Epidural Analgesia (routine care).

e. **Secondary Aim 4.** To compare the incidence of adverse events (i.e. postoperative hypotension, failed block) related to 4 quadrants TAP blocks (4Q-TAP) versus Thoracic Epidural Analgesia (routine care) 48 hours after CRS-HIPEC surgery.

**Hypothesis:** The incidence of adverse events (i.e. postoperative hypotension, failed block) related to 4 quadrants TAP blocks (4Q-TAP) is lower than Thoracic Epidural Analgesia (routine care) 48 hours after CRS-HIPEC surgery.

f. **Secondary Aim 5.** To compare the incidence of opioid-related adverse (i.e. respiratory depression, pruritus, sedation, delirium) events related to 4 quadrants TAP blocks (4Q-TAP) versus Thoracic Epidural Analgesia (routine care) 48 hours after CRS-HIPEC surgery.

**Hypothesis:** The incidence of opioid-related adverse events is lower in patients receiving 4 quadrants TAP blocks (4Q-TAP) versus Thoracic Epidural Analgesia (routine care) 48 hours after CRS-HIPEC surgery.

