To complicate the matter, **not all patients** who are scheduled for CRS-HIPEC surgery **are candidates to receive epidural analgesia**. A large retrospective study from our group demonstrated that close to **25% of the patients** who had HIPEC surgery at MD Anderson Cancer Center did **not receive epidural analgesia** and were treated with large amounts of intravenous opioids. The most common reasons why epidural analgesia is contraindicated in patients undergoing CRS-HIPEC are a reduced number of platelets (thrombocytopenia), anticoagulant therapies or patient refusal. Both clinical conditions are associated with an increased risk of epidural hematomas. A small fraction of patients might also refuse the placement of epidural analgesia because of concerns such as neurological complications or past experience with epidural failures.

Furthermore, intraoperative coagulation derangements and postoperative thrombocytopenia and coagulopathies are also the most common reasons why epidural catheter cannot be removed immediately after surgery because they can also increase the risk of bleeding in the epidural space. A recent study from our group has shown that most of the coagulopathies observed in CRS-HIPEC patients occur within the first 72 hours after surgery, however there are a portion of patients who remain coagulopathic at day 7 postoperatively. It is in this group of patients that the risk of catheter-related infections and epidural abscess is increased if the catheters are not removed.

While epidural analgesia may be considered the **“gold standard”** for postoperative pain management after HIPEC, **adverse events**, and need for active postoperative management make the use of this analgesia technique undesirable in some cases. Perioperative hypotension, urine retention as a result of opioids and motor weakness secondary to epidural local anesthetic administration are noted potential drawbacks that **might reduce the quality of recovery of patients**. Respiratory depression is another complication related to the administration of opioids administered into the epidural space particularly in elder patients.

Considering that a large number of patients undergoing CRS-HIPECs are not suitable candidates to receive epidural analgesia, a high failure rate, and a significant portion of patients suffer from epidural-related adverse effects, there is

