### **Adverse Event Definition**

An adverse event is any symptom, sign, illness, or experience which develops or worsens during the course of the study, whether or not the event is considered related to study drug. **Adverse events (AEs) related to the study interventions** will be recorded within the first 48 hours after the end of surgery. AEs related to the study will include postoperative hypotension needed pharmacological intervention including fluid resuscitation or temporary holding or discontinuation of epidural infusions, failed block (defined as patchy block or unilateral block needing pharmacological interventions or catheter removal), epidural space infection or abscess and epidural hemathoma.

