**Table 1 Study Event Schedule**

	Baseline (within 60 days prior to surgery)	Day of surgical Procedure	First 48 hours after surgery	Procedures until Discharge	Procedures After Discharge
Informed Consent	X a				
Inclusion / Exclusion Criteria Assessment	X				
Demographics/ Medical History	X				

Randomization and Intent to Treat		X b			
Vital Signs	X c	X c			
Physical Examination	X				
Laboratory Tests	X d				
Data collection	X e	X e	QoR15, pain scores, opioid consumption,	QoR15, pain scores, opioid consumption, LOS	QoR15, pain scores, opioid consumption,
Adverse Events		X f	ORADE, AE, SAE, complications (Clavien-Dindo)		

a After confirmation of eligibility and 30 days after surgery.

b After confirmation of eligibility and before surgery.

c Height, weight, systolic/diastolic blood pressure, heart rate, and respiratory rate (height and weight will only be measured at baseline)

c Data will be collected from the patients standard of care lab tests. These typically include creatinine, platelet and white blood cells count, and hemoglobin and hematocrit

d Complete blood counts, routine electrolyte determinations and renal function laboratory tests collected

e ORADE: opioid related adverse effects, AE: adverse events, SAE: serious adverse events, QoR: quality of recovery, LOS: length of stay

f During surgery, at PACU discharge and POD1 and 2.

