## Adverse Events

### General

All adverse events (AE) and serious adverse events (SAE) will be monitored from the time of procedure through end of the study.

An AE is defined as any undesirable clinical occurrence in a patient whether or not it is considered to be device related. In addition, the definition of AE applies to any event with an onset post study procedure or to any underlying diseases, present at baseline, that exacerbate in severity post study procedure. Therefore, an underlying disease that was present at the time of enrollment is not reported as an AE, but any increase in the severity of the underlying disease is to be reported as an AE. All reported AEs must be recorded in the database. A description of the event, including the start date, resolution date, action taken, and the outcome should be provided, along with the Investigator's assessment of the relationship between the AE, the study treatment and the study procedure. This protocol will use common terminology criteria for adverse events (CTCAE) version 4.0. For the AEs not characterized in the CTACE, the following definitions for rating severity of AEs will be used:

Mild: Awareness of signs or symptoms, but easily tolerated; are of minor irritant type; causing no loss of time from normal activities;

- symptoms would not require medication or a medical evaluation;  
signs or symptoms are transient.
- Moderate: Interferes with the patient's usual activity and/or requires symptomatic treatment.
- Severe: Symptom(s) causing severe discomfort and significant impact of the patient's usual activity and requires treatment.

A serious adverse event (SAE) is defined as an event which leads to:

- Death due to any cause
- Life-threatening condition
- Results in persistent or significant disability/incapacity
- Requires in-patient hospitalization or prolonged hospitalization
- Necessitates an intervention to prevent a permanent impairment of a body function or permanent damage to a body structure
- Results in congenital abnormality

All SAE's will be reported.

***Device-Related Adverse Event:*** Not applicable

***Procedure-Related Adverse Event:*** an adverse event is considered to be procedure-related when, in the judgment of the Investigator; it is reasonable to believe that the event is associated with the assigned study procedure. Other products, surgical techniques, or medications required specifically for the procedure are likely to have contributed to the occurrence of the event.

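### The plan gives conflicting collection windows for intervention-related adverse events, and the 48-hour rule can miss late epidural infection, abscess or hematoma

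*Combined protocol and SAP*

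**What the plan says.** Three places set a window for collecting adverse events.

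- **Adverse Event Definition (under Outcomes definitions).** Events related to the study interventions "will be recorded within the first 48 hours after the end of surgery". The list that follows covers hypotension needing intervention, failed block, and "epidural space infection or abscess and epidural hemathoma".
- **Table 1 Study Event Schedule.** Footnote f to the adverse-event row reads "During surgery, at PACU discharge and POD1 and 2". The row itself has an entry on the day of surgery and one in the first-48-hours column, and the two later columns appear empty.
- **The General part of the Adverse Events section.** Here every adverse event, serious or not, falls under a longer rule: such events "will be monitored from the time of procedure through end of the study". The Synopsis places that end at day 30: "The study will be considered complete after all randomized patients have had 30 days of follow-up data collection".

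Secondary Aim 4 (Study Aims) concerns adverse events related to the two techniques and gives hypotension and failed block as the events meant. Its hypothesis is that the incidence with 4Q-TAP "is lower than Thoracic Epidural Analgesia (routine care) 48 hours after CRS-HIPEC surgery".

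The Safety paragraph under Secondary Outcomes Analyses calls for separate tables of all reported, procedure-related and serious events, compared between arms by Fisher's exact test. It states no time window.

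**The concern.** Staff following the Adverse Event Definition would stop recording intervention-related events at 48 hours. Staff following the General section would continue to day 30. The two rules give different counts for the same patient.

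The difference matters most for the epidural-specific harms on the list. The Background (section B, on thoracic epidural analgesia) explains that coagulopathy can prevent prompt catheter removal. It reports that most coagulopathy falls within 72 hours of surgery but that "there are a portion of patients who remain coagulopathic at day 7 postoperatively", and that infection and abscess become more likely in this group if the catheter stays in. The plan thus names abscess and hematoma as outcomes but can stop looking while a catheter is still in place.

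At stake are the completeness of the intervention-related event outcome and the meaning of the safety tables. The primary endpoint is not affected.

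**Working it through.** No statistical figure is involved, so the check is a comparison of the passages.

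**1. Do the windows conflict in current text?** Yes. The Adverse Event Definition closes at 48 hours for intervention-related events. The General section covers all adverse and serious adverse events, which includes intervention-related ones, and runs to day 30. No sentence says that one rule serves Aim 4 and the other serves general safety.

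**2. Which side does the schedule support?** Footnote f stops at postoperative day 2, which agrees with the 48-hour rule. The empty later columns point the same way, but the table is broken in the text available, so they carry little weight. The footnote is the firmer evidence, although it is attached to the day-of-surgery entry.

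**3. Can a catheter outlast the window?** Yes. Protocol and procedures leaves removal to routine care and gives no time. The Background describes patients whose coagulopathy delays removal, some of them still coagulopathic at day 7. The documents therefore allow catheter exposure to continue after recording has stopped.

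**4. What happens to an epidural abscess found after day 2?**
- Adverse Event Definition: it is a listed event but falls outside the window, so it is not counted as intervention-related.
- Schedule footnote: no adverse-event assessment is planned at that time.
- General section: it is recorded and its relationship to the study procedure is assessed.
- Safety tables: it is included only if the General section was followed.

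**5. In which direction does the loss run?** The Background's description of the 4Q-TAP block says that it does not carry the risk of epidural hematoma or infection. Losing late epidural events therefore lowers the count in the epidural arm only. Aim 4 expects fewer events with 4Q-TAP, so this works against its hypothesis. The direction is likely rather than certain, because the 48-hour rule also cuts off late block-related events. The Background lists abdominal wall hematoma and local anesthetic toxicity as rare complications of the block, and gives liposomal bupivacaine a duration of 48 to 72 hours.

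**6. How many events would be missed?** This cannot be derived. The Background gives timing for coagulopathy, but neither timing nor rates for abscess or hematoma.

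**The case against.** The strongest reply is that late events have other routes into the trial.

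- The General section requires all reported events to be entered with an assessment of their relationship to the procedure, and the Synopsis makes all reported adverse events the primary safety endpoint.
- A late abscess or hematoma that prolonged the stay, or needed intervention to prevent permanent damage, would be a serious adverse event and reportable within 24 hours under the investigator reporting rules.
- Data collection and measurements gathers Clavien-Dindo complications during admission and morbidity data from medical records, with a 30-day point.
- The Safety tables carry no 48-hour limit.

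This stands. A reader might infer that the trial would count almost no late abscesses or hematomas whatever their true frequency. The documents do not support that, because these routes remain open.

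It can also be said that Aim 4 names only hypotension and failed block, for which 48 hours is coherent. That stands too: abscess and hematoma enter only through the Adverse Event Definition. The 48-hour phrase in the aims is weak evidence of a deliberate cutoff, since the aim on quality of recovery at days 3, 7, 10 and 30 carries the same phrase.

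The reply does not remove the contradiction. The definition that lists abscess and hematoma closes at 48 hours, and nothing says which window feeds the Fisher comparisons.

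**Conclusion.** The point holds as a contradiction between sections that has a practical consequence. If the Adverse Event Definition is followed as written, late epidural infection, abscess or hematoma is left out of the intervention-related outcome, and the procedure-related and serious event comparisons rest on an unstated window. The likely effect is to understate epidural harms. The size is unknown.

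Three stronger readings should be avoided:

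- The 48-hour window's share of the 30-day follow-up is not a measure of the loss. It is a fraction of time, not of events.
- The Background does not state an abscess risk period ending at day 7. It says that some patients are still coagulopathic then, and that risk rises if the catheter stays in.
- The gap does not create a false safety advantage for 4Q-TAP. Missing epidural events would work the other way.

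The conclusion assumes that some catheters stay in beyond 48 hours. The documents allow this but do not quantify it.

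**What to change.** 1. Keep the 48-hour window for hypotension and failed block, the events that Aim 4 names.
2. In the Adverse Event Definition, record epidural infection or abscess, epidural hematoma and other procedure-related events in both arms to day 30.
3. Align the adverse-event row and footnote f of the Study Event Schedule with the General section.
4. In the Safety paragraph under Secondary Outcomes Analyses, state that the procedure-related and serious event tables use the 30-day window.

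The cost is a wording amendment, a longer eCRF window and a little more chart review within the existing day-30 follow-up. The sample size and the primary analysis do not change.

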#### *4-quadrant TAP block*

**To enhance the analgesic efficacy of the traditional TAP block**, several authors have added a subcostal approach to provide analgesia to the upper half of the abdomen. In a cadaveric study of the four-quadrant TAP block (4QTAP), dermatomes T8-L1 were adequately covered with the solution of local anesthetic. Therefore, it was originally hypothesized that the 4QTAP block may be more beneficial in major abdominal surgery compared to the traditional TAP approach alone. In a prospective study of 124 patients, the surgical incision for abdominal surgery was within the dermatomal limits of the 4QTAP in 70% of patients. In a later study by Niraj et al, the authors demonstrated that 4QTAP with levobupivacaine resulted in similar pain scores and tramadol consumption when compared to epidural analgesia for laparoscopic colorectal surgery.

**The 4QTAP block may provide some advantages over epidural analgesia** as TAP blocks are associated with more stable hemodynamics and less use of vasopressor and intravenous fluids during and after surgery. In addition, 4QTAP blocks are not associated with postoperative urine retention neither the risk of epidural hematoma or infections. Lastly, the use of 4QTAP blocks can reduce the use of resources and personnel because there is no need for frequent monitoring of the epidural catheter and infusions pumps.

With the increased safety of ultrasound guided needle placement and 'real-time' visualization through dynamic scanning, **serious complications are rare** with the 4QTAP block. Needle puncture thru the peritoneum causing bowel or diaphragm perforation is unlikely, but is still a possibility. The abundance of structures in the peritoneal cavity makes the viewing of the needle in plane at all times during needle advancement of utmost importance. Lacerations of the liver have been reported during placement of right-sided TAP blocks. Abdominal wall hematoma, vascular injury, local anesthetic toxicity and are also potential, but rare complications.

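### The adverse-event definition behind secondary Aim 4 is asymmetric between the arms and may tilt the comparison towards the hypothesised lower rate with 4Q-TAP

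*Combined protocol and SAP*

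**What the plan says.** Aim 4 (section 3, Study Aims) is directional: "The incidence of adverse events (i.e. postoperative hypotension, failed block) related to 4 quadrants TAP blocks (4Q-TAP) is lower than Thoracic Epidural Analgesia", within 48 hours of surgery. The events related to the interventions are defined in one place, Adverse Event Definition, under Outcomes definitions. The first item is "postoperative hypotension needed pharmacological intervention including fluid resuscitation or temporary holding or discontinuation of epidural infusions". The rest are "failed block (defined as patchy block or unilateral block needing pharmacological interventions or catheter removal), epidural space infection or abscess and epidural hemathoma".

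The background section on the 4-quadrant TAP block names harms of that technique: perforation of bowel or diaphragm, liver laceration, and then "Abdominal wall hematoma, vascular injury, local anesthetic toxicity and are also potential, but rare complications". None of these is in the list. The Interventions section describes 4Q-TAP as injections into four quadrants before incision and mentions no catheter.

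Two other sections bear on the point. Adverse Events (General) requires all reported events to be entered, with the investigator's view of their relation to treatment and procedure. The Safety paragraph under Secondary Outcomes Analyses gives procedure-related events their own table and compares event rates by Fisher's exact test.

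**The concern.** For the same clinical course, a TEA patient has more ways to score an event than a TAP patient, and the aim predicts exactly that direction. The component most likely to matter is failed block, and three features of the plan make it doubtful that an ineffective TAP block would be counted:

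- Protocol and procedures makes opioid boluses, with patient-controlled analgesia if needed, the planned postoperative analgesia for everyone. A need for drug treatment therefore does not by itself mark a failed TAP block.
- Incision-site pain in the first 48 hours is, by default, not an adverse event (list of exclusions under Adverse Events).
- No assessment of sensory block is described in either arm, so nothing specified would show a TAP block to be patchy or one-sided.

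At stake is a comparative safety claim for 4Q-TAP that could come partly from the counting rule.

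**Working it through.** **1. The list, item by item**

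| Item | Open to TEA | Open to 4Q-TAP |
|---|---|---|
| Hypotension treated with drug or fluid | yes | yes |
| Hypotension handled by holding or stopping the epidural infusion | yes | no |
| Patchy or unilateral block needing drug treatment | yes | yes, if the wording is applied to TAP |
| Failed block leading to catheter removal | yes | no |
| Epidural infection or abscess | yes | no |
| Epidural hematoma | yes | no |
| Any complication specific to TAP | – | none listed |

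The aim names only hypotension and failed block in its parenthesis, and the plan does not say whether Aim 4 is tested on those two items or on all four. On the narrower reading the asymmetry lies only in the two epidural-only limbs and in how failed block is applied to TAP.

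**2. How much could failed block matter?**

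The plan gives no expected rate, power or sample size for Aim 4, so there is no figure to reproduce. Inputs for an illustration:

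- *n* = 80 per arm (Synopsis).
- True failure rate *p* = 10% to 30%, the range the background gives for failure of epidural catheter placement. It sets the scale only, because placement failure is not the same as patchy or unilateral block.
- Assumed: the same *p* in both arms; all TEA failures counted; a share *c* of TAP failures counted. The documents give neither the TAP failure rate nor *c*.
- Assumed: two-sided 0.05. The plan states no level for Fisher's test.

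With *X* ~ Bin(*n*, *p*) counted failures on TEA and *Y* ~ Bin(*n*, *cp*) on TAP,

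P(false TAP-lower result) = Σ P(X = x) P(Y = y) over all pairs with x > y and Fisher p ≤ 0.05.

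| Share *c* of TAP failures counted | *p* = 10% | *p* = 20% | *p* = 30% |
|---|---|---|---|
| 1 | 1.4% | 1.6% | 1.7% |
| 0.75 | 4.8% | 9.2% | 14.5% |
| 0.5 | 14.2% | 34.8% | 56.3% |
| 0.25 | 37.2% | 79.3% | 95.2% |
| 0 | 82.3% | 99.9% | about 100% |

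The bottom row can be checked by hand. With no TAP events, two-sided Fisher p = 2·C(80, k)/C(160, k) for *k* TEA events: k = 5 gives 0.059 and k = 6 gives 0.028, so six events suffice. P(X ≥ 6) for Bin(80, 0.10) is 0.823. The expected count, 8/80 against 0/80, gives p = 0.0065.

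With 70 per arm (half of the 140 in the Statistical Considerations), the 10% column becomes 1.3%, 4.0%, 11.4%, 30.2% and 71.3%.

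**The case against.** A reader might infer that the definitions guarantee a lower TAP rate, with an 82% chance of a false significant result. The documents do not support that. The figure requires that no TAP failure is ever counted, whereas the words patchy and unilateral name no technique. A block made of four injections can miss a side or a quadrant, and the background reports that the incision lay within the dermatomal limits of the four-quadrant block in only 70% of patients in one series. If such blocks are counted in full, the tilt from this component largely disappears.

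Other points on that side also stand:

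- The 10% to 30% refers to catheter placement. The background treats poorly functioning but correctly placed catheters separately and gives no rate for them.
- An epidural that never works is neither patchy nor unilateral. Unless catheter removal counts alone, it too may escape the definition, which pulls the other way.
- Epidural abscess and hematoma are genuine harms of the comparator, and few would be expected in 160 patients.
- The list is introduced as what the events will include, so it need not be exhaustive. TAP complications would be recorded and would reach the procedure-related table, which might be read as the Aim 4 analysis.

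This limits the size and reach of the point but does not remove it. No text links the procedure-related table to Aim 4, no rule says how a TAP block is judged patchy or unilateral, and an ineffective TAP block may surface only as pain, which is excluded by default.

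**Conclusion.** The asymmetry is plain on the text: two of four items are possible only with TEA, the other two each have a TEA-only limb, and no TAP complication is listed. It may tilt Aim 4 towards its hypothesis. This is a structural tilt, not a measured bias. Its size depends mainly on the share of failed TAP blocks that is counted. With 80 per arm and equal true failure rates, the chance of a false TAP-lower result on that component runs from 1.4% (all counted) through 14% (half) to 82% (none) at 10% failure, and from 1.7% through 56% to about 100% at 30%. Equal rates, the share counted and the two-sided 0.05 level are assumptions.

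The consequence is confined to one secondary safety comparison. TAP harms are not lost to the trial, and the primary QoR-15 test and its sample size are untouched.

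**What to change.** For the between-arm Aim 4 test, count only events that can occur in both arms, with outcome definitions applied identically:

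- **Hypotension:** the drug-or-fluid limb alone, without the epidural-only limb.
- **Failed block:** one pre-specified criterion of inadequate analgesia, assessed in the same way in both arms. It should depend neither on a catheter nor on the mere use of the opioid boluses or patient-controlled analgesia planned for all. Pain scores and breakthrough-medication requirements, both already in Data collection and measurements, could supply it.

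Add the TAP complications named in the background to the event list. Report technique-specific events, epidural and TAP alike, descriptively by arm and outside the test. State which table is the Aim 4 analysis.

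The cost is mainly protocol and eCRF wording. Postoperative vasopressor and fluid treatment may need a field: the collection list has no vasopressor item and records fluid therapy only at the end of surgery. The contrast may also look less favourable to 4Q-TAP. These are outcome definitions and change no treatment.
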